**Objective:**

The main objective of this research was to carry out an experimental study, triple blind, on the possible immunophysiological effects of a nutritional supplement (Synbiotic, Gasteel Plus®, Heel España S.A.U.), containing a mixture of probiotic strains, such as *Bifidobacterium lactis* CBP-001010, *Lactobacillus rhamnosus* CNCM I-4036, *Bifidobacterium longum* ES1, as well as prebiotic fructooligosaccharides, in both professional athletes and sedentary people.

**Design:**

This investigation was a triple blinded, randomized, placebo-controlled pilot study designed to identify the possible differing effects of the synbiotic Gasteel Plus® supplementation between sedentary individuals and soccer players. Subjects were asked to maintain their regular lifestyle and the participants were prohibited from consuming probiotics, prebiotics or fermented products (yogurt or other foods) to avoid unnecessary interference during the experimental periods. Presenting injury or illness would result in exclusion from the study. All participants were also asked to provide written informed consent before participating in the study, which had been previously approved by the ethics committee of the Catholic University of Murcia (Spain) following current legislation (CE031810).

On two separate days, the "baseline-tests" and "final-tests" were conducted. All participants performed a series of tests, before which they had to fast. The order and schedule (8 am) of the tests was the same for the "final-test" and the same materials and procedures were used. A period of 30 consecutive days elapsed between the base-line and final tests, during which the participants had to ingest their supplement (synbiotic or placebo). Accelerometers were distributed one week prior to the baseline test and the week after the final test. Blood and saliva sampling were taken early in the morning and questionnaires were filled out on the two testing days. The treatment was carried out during the last fortnight of May 2019 and the first fortnight of June of the same year, coinciding with situations of possible physical and mental stress in both participant groups, being at the end of an examination period, as well as the end of the soccer season.

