### **Statistical Analysis Plan (SAP):**

Statistical analysis was performed with IBM statistics SPSS v20.0 software (SPSS Inc., Chicago IL, USA). To verify the normality of the data, the Shapiro-Wilk test was performed. The repeated two-way analysis of variance (ANOVA) was used, followed by Student's paired and unpaired t-tests to analyze the intervention effect. The values were expressed as mean  $\pm$  standard deviation (SD) and the significance level was considered when  $p<0,05$ .

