It should be noted that both groups presented healthy baseline levels of the inflammatory and immune parameters analysed. No significant differences in the IL-1 $\beta$  concentrations were observed between the sedentary and athlete groups. However, a different behaviour ( $p<0.05$ ) between the two groups was found in response to the synbiotic intervention: while the synbiotic increased ( $p<0.05$ ) the systemic concentration of IL-1 $\beta$  in the sedentary group, it slightly decreased in the soccer player group.

No significant variations (except a potential placebo effect in the sedentary group) were found in the IL-10 concentration. There were also no significant differences in the levels of immunoglobulin A between groups, or as a consequence of the intervention.

A lower concentration without significant differences were found in the dopamine concentration of the soccer players group. However, training affected the response to the synbiotic intervention ( $p<0.05$ ), since it induced a significant increase ( $p<0.05$ ) in the dopamine concentration only in the athletes. This effect cannot be attributable to a potential placebo effect of the intervention. However, the decrease ( $p<0.05$ ) in epinephrine levels in the sedentary group administered with the synbiotic compared to their basal levels could potentially be attributed to a placebo effect of the intervention. In addition, there were also no significant changes in norepinephrine. Basal concentration of serotonin was, however, higher ( $p<0.05$ ) in the athlete group than in the sedentary group, but statistical differences with the synbiotic intervention were not observed.

Finally, the results corresponding to CRH showed a lower systemic concentration of CRH than sedentary volunteers. In addition, the behaviour of CRH secretion in response to the synbiotic intervention was also different ( $p<0.05$ ) between the athlete group and the sedentary group, decreasing significantly ( $p<0.05$ ) in the sedentary group with respect to their baseline levels (as also found with the placebo) and increasing slightly in the athlete group. The latter cannot be attributable to a placebo effect of the intervention. There were no significant differences in levels of cortisol and ACTH between groups or as a consequence of the intervention.

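### No stabilisation period is documented between the start of the dietary ban and the baseline test, so within-arm changes, and athlete-versus-sedentary comparisons of them, may include withdrawal of fermented foods

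*Combined protocol and SAP*

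**What the plan says.** The Design section sets the dietary rule: "the participants were prohibited from consuming probiotics, prebiotics or fermented products (yogurt or other foods) to avoid unnecessary interference during the experimental periods". Alongside it, "Subjects were asked to maintain their regular lifestyle". No start date, washout or run-in is given, and no recording of habitual probiotic or fermented-food intake is described.

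On timing, the same section states: "A period of 30 consecutive days elapsed between the base-line and final tests, during which the participants had to ingest their supplement". The only study activity placed before baseline is activity monitoring: "Accelerometers were distributed one week prior to the baseline test and the week after the final test". The text does not say whether the ban covered either accelerometer week.

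On control: "This investigation was a triple blinded, randomized, placebo-controlled pilot study". The ban is worded for all participants, so it applies to both arms.

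The SAP section plans a repeated two-way ANOVA without naming its factors, "followed by Student's paired and unpaired t-tests to analyze the intervention effect". It does not name a synbiotic-versus-placebo difference in change as the treatment effect.

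The Results section mostly reports change from baseline within an arm, and differences in response between athletes and sedentary people. The placebo arm serves as an informal check. For example, the fall in epinephrine in the sedentary synbiotic group "could potentially be attributed to a placebo effect of the intervention".

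**The concern.** Suppose the ban took effect at or shortly before the baseline test. Baseline blood, saliva and questionnaires would then reflect each person's usual intake of live cultures and fermented foods, while the final measurements would follow 30 days without them. A habitual yogurt eater given placebo goes through withdrawal. The same person given synbiotic goes through withdrawal plus supplement. A non-consumer given synbiotic goes through supplement alone.

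Three readings are exposed.

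- **Paired tests within the synbiotic arm.** The change they test is not the supplement effect alone.
- **Athletes versus sedentary people.** A differing response in these two populations is the stated purpose of the study. The populations are not randomised and may differ in habitual intake. Different amounts of withdrawal could then look like a different response to the supplement.
- **The term placebo effect.** The Results use it for IL-10 and epinephrine in sedentary people, and note that the fall in CRH also occurred on placebo. A change in the placebo arm may reflect the restriction, the calendar or expectation, and this design cannot separate them.

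Starting the ban with the first accelerometer would not fully resolve this. The Methods say that the Perceived Stress Scale covers the last month. With a 30-day month, 30 − 7 = 23 days of the baseline recall would precede the ban, whereas the final recall would fall within it.

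**Working it through.** The plan states no sample size, power or effect size, so there is no figure to reproduce. The check has an algebraic part, which follows from the design, and a numerical part, which is an illustration.

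**1. What each contrast contains.** Assume the ban starts at baseline. Let s be the supplement effect, w the mean effect of stopping fermented foods, and t the effect of time (season, exams, repeat testing).

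- Synbiotic-arm change = s + w + t
- Placebo-arm change = w + t
- Synbiotic minus placebo = (s + w + t) − (w + t) = s

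The last line needs w to be equal in the two arms in expectation, which randomisation provides, and s not to depend on prior intake.

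**2. The two populations.** With subscripts A (athletes) and S (sedentary):

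- Within the synbiotic arm only: (s_A − s_S) + (w_A − w_S) + (t_A − t_S)
- With the placebo arms subtracted first: s_A − s_S

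A difference in habitual intake therefore distorts the first contrast and drops out of the second.

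**3. Illustration.** From the SAP: significance level 0.05. Assumed: two-sided tests, normal changes, 6 to 20 people per arm, w of 0.25 to 0.8 in units of the SD of the change, and s = t = 0. Any significant result is then false as evidence for the supplement.

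*Paired test in one arm.* P = 1 − F(c) + F(−c), where F is the noncentral t distribution with n − 1 degrees of freedom and noncentrality w√n, and c is the two-sided 5% critical value. For n = 10 and w = 0.5, the noncentrality is 0.5 × √10 = 1.58 and P = 29.3%.

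*Synbiotic significant, placebo not.* The arms are independent with the same w, so the probability is P(1 − P). For n = 10 and w = 0.5 this is 0.293 × 0.707 = 0.207. With w = 0 it is 0.05 × 0.95 = 0.0475, or 4.8%.

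*Athletes versus sedentary, synbiotic arm only, withdrawal in one population only.* Unpaired test with 2n − 2 degrees of freedom and noncentrality w/√(2/n). For n = 10 and w = 0.5 this is 0.5/√0.2 = 1.12, and the rejection probability is 18.5%.

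| n per arm | w | Paired test significant | Synbiotic significant, placebo not | Populations differ, synbiotic arm only |
|---|---|---|---|---|
| 6 | 0.25 | 8.0% | 7.3% | 6.8% |
| 6 | 0.5 | 17.1% | 14.2% | 12.3% |
| 6 | 0.8 | 35.6% | 22.9% | 24.1% |
| 10 | 0.25 | 10.9% | 9.7% | 8.3% |
| 10 | 0.5 | 29.3% | 20.7% | 18.5% |
| 10 | 0.8 | 61.6% | 23.6% | 39.5% |
| 15 | 0.25 | 14.7% | 12.6% | 10.1% |
| 15 | 0.5 | 43.8% | 24.6% | 26.2% |
| 15 | 0.8 | 82.1% | 14.7% | 56.2% |
| 20 | 0.25 | 18.6% | 15.1% | 12.0% |
| 20 | 0.5 | 56.5% | 24.6% | 33.8% |
| 20 | 0.8 | 92.4% | 7.0% | 69.3% |

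A direct test of synbiotic against placebo change stays at 5% in every row, because w is the same in both arms.

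**4. What a washout would add.** If the ban started early enough that w = 0 after baseline, the paired test would return to 5% only if t = 0 as well. The Design section itself says that the study coincided with stressful periods, at the end of exams and of the soccer season, so t = 0 is doubtful. The between-arm contrast is needed with or without a washout.

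**The case against.** The strongest reply is that the trial has a randomised, blinded placebo arm under the same ban. A concurrent control need not be stable; it has to undergo the same influences apart from the treatment. Withdrawal cancels on average in the synbiotic-versus-placebo comparison, and in the population comparison too once placebo change is subtracted. This stands. A reader might infer that the ban biases every comparison in the trial, and the documents do not support that. The harm is confined to readings that leave the placebo arm out, and to the meaning of s if the supplement acts differently in people who have just stopped fermented foods.

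A second reply is that the documents are silent on when the ban began. The undefined term may include the accelerometer week or an earlier time. This also stands: a reader might infer that there was no run-in, but what can be said is that none is documented.

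Third, the placebo-arm changes do not show that the ban acted. The end of exams and of the season explains them equally well. The ones reported (activity, IL-10, CRH) are in sedentary people, and athletes on placebo showed no significant accelerometer changes.

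Fourth, the trial is finished, so a longer ban cannot be added. That limits the fix for this trial but does not affect the analysis and wording changes.

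The reply does not remove the fact that the SAP offers paired tests as a way to assess the intervention effect, leaves the ANOVA factors unnamed, and leads to results read mainly from within-arm change. In the Results, the one explicit mention of the two-way ANOVA concerns athlete-versus-sedentary response to the synbiotic. The text does not say whether placebo change was subtracted.

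**Conclusion.** The point holds in limited form. No stabilisation period before baseline is documented. If the ban began at or near baseline, within-arm changes and athlete-versus-sedentary comparisons of them may include withdrawal of fermented foods. The synbiotic-versus-placebo comparison of change is protected on average, but the plan does not make it the stated basis for the treatment effect.

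The actual size is unknown. Over the assumed range of 6 to 20 per arm and shifts of 0.25 to 0.8 SD of the change, a paired test would be falsely significant in 8% to 92% of trials. The pattern of synbiotic significant and placebo not would arise in 7% to 25%, against 4.8% with no shift. A synbiotic-arm comparison of populations would falsely reject in 7% to 69% if only one population had withdrawal. These figures show how the tests behave and do not estimate what happened here: the documents give neither sample size nor habitual intake, and a true shift near zero would leave the tests near nominal.

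One might also infer that the ban caused the changes seen on placebo. The documents do not support that, but neither do they support calling those changes a placebo effect. The point merits a change to the plan and to the wording of the Results; it does not invalidate the randomised comparison.

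**What to change.** **Design, for a repeat or later trial.** Start the ban at a fixed, stated time before baseline, no later than the hand-out of the first accelerometer, and keep it until the second accelerometer is returned. The documents support no specific length, so the sponsor should choose one and justify it. At screening, record habitual probiotic and fermented-food intake (yes/no and servings per week) and use it as a covariate.

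**SAP.** Name the ANOVA factors. Base the treatment effect on the synbiotic-versus-placebo difference in change (arm × time), and the differing response on arm × population × time. Keep within-arm paired tests as description only.

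**Results.** Replace the term placebo effect with wording such as: change over the period in the placebo arm, which may reflect the dietary restriction, the end of exams or season, or expectation.

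**For the completed trial.** Only the analysis and wording changes, and a statement of when the ban began, can be applied. The analysis and wording changes need no new data.

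**Cost.** A longer dietary restriction and one extra screening question, so slightly more burden for participants. No extra visit or assay is needed.

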**Methods:**

Objective determination of levels of physical activity, sedentary lifestyle and sleep quality: accelerometry

The accelerometer used was the Actigraph wGT3X-BT, which is a small and light triaxial accelerometer (4.6 x 3.3 x 1.5 cm, 19 g) with a response frequency of 30 to 100 hertz. This device was used to measure different objective parameters such as physical activity and its intensity, energy expenditure, metabolic equivalents rhythms (MET), weekly steps, sedentary bouts and sleep latency and efficiency. Participants wore the accelerometer held with an elastic band on the non-dominant wrist for 7 consecutive days and without interruption, except for those times of the day in which the correct operation of the device could be compromised (showers or any activity related to water). Subsequently, the files generated by the accelerometer were analyzed through a specific software called Actilife 6 (Actigraph, Pensacola, USA).

Determination of perceived levels of general health, stress, anxiety, fatigue, depression and sleep quality: questionnaires

Participants had to fill out a series of validated questionnaires to identify possible subjective health and mental states.

SF-36 Questionnaire. This is an instrument that provides results about the health status of a general population covering 8 scales: physical function, physical role, body pain, general health, vitality, social role, emotional role and mental health. The scales are ordered so that the higher the score, the better the health status (0 to 100).

Sleep Quality in Healthy Lifestyle and Personal Control Questionnaire (HLPCQ). The HLPCQ is a questionnaire whose main objective is to detect and quantify lifestyle patterns that reflect health empowerment, as evidenced by the levels of stress and of the internal locus of control. It also includes a section with various questions to measure sleep quality where higher scores indicate better sleep quality.

The State-Trait Anxiety Inventory (STAI). This questionnaire analyzes the degree of anxiety that each participant shows. It is divided into two parts: trait-anxiety (what they usually or generally felt) and state-anxiety (their expressed emotions at a specific moment), in which higher scores indicate a higher state of anxiety.

The Perceived Stress Scale (PSS). This questionnaire allowed the frequency at which individuals had experienced certain stressful feelings to be assessed, as well as their thoughts in the last month.

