### Results:

Among the most important results we can observe:

the sedentary group administered with placebo obtained some significant differences with respect to baseline values ( $p<0,05$ ). A decrease in calories, metabolic rate and intensity level of physical activity are reflected. The synbiotic seems to prevent this situation by avoiding the mentioned decreases and even increasing the consumption of Kilocalorie (Kcal) in sedentary individuals although without significant differences. Results from the athlete group show no significant changes ( $p>0,05$ ) in those who consumed placebo, while those who followed the protocol with the intake of the synbiotic had significant improvements in sleep efficiency and latency, as well as increases in the consumption of Kcal and METS.

The baseline values are quite similar in the sedentary and athlete groups. Only in the athletes did the synbiotic intervention significantly improve ( $p<0,05$ ) the perceived general health as determined by the SF-36 questionnaire, but no differences were found in perceived sleep quality, state anxiety, and fatigue.

No significant differences were found in the perceived stress, trait anxiety, and depression between sedentary people and athletes at basal status (before intervention). The results show a decrease in the levels of perceived stress ( $p<0.01$ ) and anxiety ( $p<0.05$ ) only in the athlete group administered with the synbiotic. Also shows a decrease ( $p<0.05$ ) in perceived depression levels in both groups (sedentary and athlete) after the synbiotic treatment. Then, training only affected the behavior in response to the synbiotic intervention in stress and particularly in anxiety ( $p<0.05$ ) also when evaluating by the two way ANOVA test). These effects were not due to a placebo effect.

The results corresponding to blood concentrations of glucose, cholesterol, and triglycerides as measurements of metabolic profile. Firstly, individuals in both the sedentary and athlete groups presented lipid and glycaemic levels compatible with normal and healthy ranges. Thus, as expected the consumption of the synbiotic did not provoke an appreciable or significant effect

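### As described, the follow-up accelerometer week falls after the 30-day intake period, so the activity and sleep outcomes measure what remains after supplementation, and the Results do not say so

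*Combined protocol and SAP*

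**What the plan says.** The Design section fixes the intake window: "A period of 30 consecutive days elapsed between the base-line and final tests, during which the participants had to ingest their supplement". It also dates the treatment: "The treatment was carried out during the last fortnight of May 2019 and the first fortnight of June of the same year". For the devices it states: "Accelerometers were distributed one week prior to the baseline test and the week after the final test". Blood, saliva and questionnaires are tied to the two test days.

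The accelerometry part of Methods gives the wear time: "Participants wore the accelerometer held with an elastic band on the non-dominant wrist for 7 consecutive days". It lists the outcomes taken from the device: physical activity and its intensity, energy expenditure, METs, steps, sedentary bouts, sleep latency and sleep efficiency.

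The SAP names a repeated two-way ANOVA followed by "paired and unpaired t-tests to analyze the intervention effect". It says nothing about when the accelerometer data were collected.

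The Results state that "the sedentary group administered with placebo obtained some significant differences with respect to baseline values", namely falls in calories, metabolic rate and activity intensity. They then say: "The synbiotic seems to prevent this situation by avoiding the mentioned decreases". For athletes on the synbiotic they report "significant improvements in sleep efficiency and latency, as well as increases in the consumption of Kcal and METS", and for athletes on placebo no significant change. The timing of the follow-up week is not mentioned there, and no synbiotic-minus-placebo estimate or interval is given for these outcomes.

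**The concern.** If intake ends at the final test and the second wear week follows it, the device never records participants while they are taking the supplement. The accelerometer outcomes then answer whether anything persists in the week after supplementation. A reader of the Results would naturally take them as effects during intake. An effect present during intake could be diluted by an unknown amount.

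The placement is also asymmetric: the baseline week precedes its test and the follow-up week comes after its test. This pushes follow-up further past the end of the examination period and the soccer season, when activity and sleep may change for reasons unrelated to the supplement. Within-arm before/after changes, on which the accelerometer statements mainly rest, are fully exposed to such shifts. The significant falls in the sedentary placebo arm show that these outcomes can move without the synbiotic.

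Finally, the Results set the accelerometer outcomes beside blood, saliva and questionnaire outcomes collected at the end of intake, without saying that the two sets differ in exposure.

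**Working it through.** **Inputs.** Intake: 30 consecutive days between the tests (Design). Treatment dates: last fortnight of May and first fortnight of June 2019 (Design). Second device hand-out: the week after the final test (Design). Wear: 7 consecutive days (Methods).

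**Step 1: does the 30-day figure agree with the dates?**
- Two 14-day fortnights: 14 + 14 = 28 days.
- Two half-months of 15 days: 15 + 15 = 30 days.
- 16–31 May plus 1–15 June: 16 + 15 = 31 days.

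The stated 30 days is reproduced exactly by the second count and lies within the 28 to 31 range.

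**Step 2: could dosing have continued through the follow-up wear week?** That would need 30 + 7 = 37 days, which exceeds the stated dates by 37 − 31 = 6 to 37 − 28 = 9 days. The 28-day count cannot hold 30 days of intake, so the counts that can hold it give a shortfall of 6 or 7 days. At most 31 − 30 = 1 day is spare.

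**Step 3: overlap of wear with intake.** Take the baseline test as day 0 and the final test as day 30. Baseline wear is days −7 to −1, with midpoint −4.

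| Follow-up wear | Days | Days on supplement | Midpoint | Gap from baseline midpoint |
|---|---|---|---|---|
| Starts on final test day, dose also taken that day | 30–36 | at most 1 of 7 | 33 | 33 − (−4) = 37 |
| Starts the day after | 31–37 | 0 of 7 | 34 | 34 − (−4) = 38 |
| Handed out at the end of that week | 37–43 | 0 of 7 | 40 | 40 − (−4) = 44 |
| Mirrors baseline (comparison) | 23–29 | 7 of 7 | 26 | 26 − (−4) = 30 |

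Calendar check of the 38-day gap on the widest dates: baseline test 16 May and final test 15 June, so baseline wear is 9–15 May and follow-up wear 16–22 June. The midpoints, 12 May and 19 June, are 38 days apart.

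**Step 4: size of any dilution.** Write the measured effect as f × (effect during intake), assuming f between 0 and 1. At f = 1 nothing is lost; at f = 0 the effect has gone by the wear week. The documents give nothing to place f in that range. A delayed or reversed effect would fall outside it.

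**The case against.** The strongest reply is that the sentence may be loose wording. It describes when devices were distributed and gives no wear dates; if the devices were in fact worn before the final test, the defect is one wrong word. That possibility stands and is why the first action is a date check. The word itself does not rescue the timing: hand-out in the week after the final test can only put wear at or after that test. The calendar dates are loose too, but the 30-day sentence is enough without them.

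Second, no bias is shown. Both arms were measured on the same schedule, so timing alone does not bias the randomised comparison, and the documents name no estimand restricted to the intake period. This is correct. A supplement-free follow-up week after a full course is a legitimate design that answers a different question. What remains is that the question answered should be stated where the results are interpreted.

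Third, the Design section discloses the timing, and the Results do not restate timing for the other outcomes either. That is fair as to concealment, which is not alleged. The accelerometer outcomes are, however, the only ones collected in a different exposure state.

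Fourth, reliance on within-arm change is a wider weakness that also touches questionnaires and blood, and it would persist with any wear week. Calendar shifts would also remain with wear on days 23–29. Both points stand, but the accelerometer claims do rest mainly on within-arm change, and the later wear week adds to their exposure.

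**Conclusion.** The concern holds as written. Follow-up accelerometer wear overlaps intake on 0 of 7 days, at most 1, and the wear-week midpoints are 38 days apart on the earliest reading that has no overlap, against 30 had follow-up mirrored baseline. The accelerometer outcomes therefore estimate a residual effect after supplementation, and the Results do not label them so.

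This rests on two assumptions: that the device sentence is accurate, and that dosing ended at the final test. The second is inferred from the 30-day sentence and the treatment dates, since no last-dose date is given. Confidence is medium for that reason. The size of any dilution is unknown. Outcomes collected on the test days are unaffected. The point changes how one family of outcomes is read; it does not invalidate the trial.

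**What to change.** **Data already collected**

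1. Confirm the last-dose dates and actual wear dates. If the devices were worn before the final test, correct the Design sentence.
2. If the sentence is accurate, label every accelerometer outcome as measured in the week after supplementation.
3. Report the synbiotic-minus-placebo difference in change with a 95% CI, separately for sedentary participants and athletes. An unpaired t-test is already named in the SAP, which should state that it is applied to change scores between arms. A between-arm difference shown this way can still be attributed to the assigned supplement. Remove only wording that rests on within-arm change or implies an effect during intake.

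The cost is a date check, a label and a re-analysis, with no new data. Some within-arm statements in the Results may no longer stand.

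**Follow-on trial**

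Place the 7-day wear in the 7 days before the final test (days 23–29), mirroring baseline, and collect devices at that test. This brings the device outcomes into line with the blood, saliva and questionnaire outcomes. It needs the same devices and wear time, plus one earlier contact to hand them out.
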